5.12.1 Primary efficacy endpoint analysis

The primary efficacy outcome is ATE, defined by one or more of the following events occurring within the time period specified above:

- ischemic stroke
- transient ischemic attack
- systemic embolism

If the patient dies before day 35 and has not had the primary event, then it will be assumed that the patient would not have had an event had he/she been followed for 35 days.

The primary endpoint analysis is a non-inferiority analysis with an absolute margin of 1.0 percent. For that reason, the statistical test must provide confidence limits for the difference in rates. The two tests available with standard software that provide corresponding confidence limits are the likelihood ratio test and Barnard's test. The likelihood ratio test does not maintain the nominal alpha level for small sample sizes, and so that test will not be used.

There is a proposed an unconditional exact test based on a minimax elimination of the nuisance parameter [38]. The reference set was defined to be the set of all 2 x 2 tables with fixed row margins and all possible column margins. The test and its associated 95 percent confidence limits will be calculated using the StatXact 7 software [39]. If the upper 95 percent confidence limit for the difference in event rates (placebo primary event rate - bridging anticoagulation primary event rate) is less than 0.01, then the primary endpoint will have been met for placebo.

5.12.2 Primary bleeding endpoint analysis

The primary bleeding endpoint is major bleeding, defined by one or more of these events:

- symptomatic or clinically-overt bleeding that is associated with one or more of a) transfusion of ≥2 units heterologous packed red blood cells or whole blood
- decrease in hemoglobin level >20 g/L (>2 g/dL)

CONFIDENTIAL

- need for re-operation or invasive intervention (e.g., evacuation of wound hematoma)
- symptomatic or clinically-overt bleeding at a critical anatomic site
- fatal bleeding

Because these outcome measures do not require the construction of confidence limits, we will use the simpler Fisher's mid-p test [40] to test significance.

5.12.3 Secondary efficacy endpoint analyses

The following 30 day endpoints will be analyzed using Fisher's mid-p test:

- acute myocardial infarction (ST- and non-ST-elevation)
- deep vein thrombosis
- pulmonary embolism
- death

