		10.1.4.1 Standard site management practices	
11.0	Adverse Even	t Reporting and Follow-up	
		s Adverse Events	
	11.1.1	Serious adverse event collection and reporting	
		Lack of efficacy	
	11.1.3	Clinical or laboratory abnormalities	
		Assessment of causality	
		Unexpected Adverse Events	
		Unanticipated Problem	
		Follow-up of SAEs	
		DCRI Safety Surveillance and Medical Monitor	
		Regulatory reporting	
12.0		o Institutional Policies on Conflict of Interest	
13.0	Prototype of I	nformed Consent	41
		t withdrawal from the BRIDGE Trial.	
14.0	Regulatory Af	ffairs	41
15.0	Scientific Rep	orting and Publication	41
16.0	References		43
Apper	ndix A		46

VERSION DATE	Amendment 1 January 28, 2009 Amendment 2 February 17, 2010		
PRINCIPAL INVESTIGATORS	[name] (Clinical Coordinating Center) [name] (Statistical Data Coordinating Center)		
CO- P RINCIPAL INVESTIGATORS	Drs. [name] and [name]		
PROTOCOL TITLE	"BRIDGE": B ridging Anticoagulation in Patients who R equire Temporary I nterruption of Warfarin Therapy for an Elective Invasive Proce d ure or Sur ge ry		
STUDY OBJECTIVES	 To compare the efficacy of bridging anticoagulation (therapeutic-dose LMWH) with no bridging anticoagulation (placebo) on the rate of ATE in patients with atrial fibrillation or atrial flutter who require temporary interruption of warfarin. To compare the safety of bridging anticoagulation with no bridging anticoagulation on the rate of major bleeding in patients who require temporary interruption of warfarin. 		
STUDY PHASE	Phase III		
STUDY DESIGN	Randomized double-blind, placebo-controlled, trial.		
TREATMENT REGIMENS	 Patients will be randomly allocated to: bridging anticoagulation arm (dalteparin ~100 units/kg SC twice-daily) or no bridging anticoagulation arm (matching placebo, SC twice-daily) for approximately 3 days before and approximately 6 days after procedure or surgery. 		
ROUTE OF ADMINISTRATION	Active study drug or placebo will be administered by subcutaneous injection.		
PATIENT POPULATION	Patients with atrial fibrillation or atrial flutter who are receiving long- term warfarin therapy and require temporary interruption of warfarin because of an elective surgical or other invasive procedure.		
PLANNED SAMPLE SIZE	3,626 patients (1,813 patients per treatment arm)		

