5.3 Classification of Type of Surgery or Procedure

Patients who satisfy the trial eligibility criteria will be classified according to the planned surgery/procedure.

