5.5.2 Randomization procedure and stratification

CONFIDENTIAL

The Statistical and Data Coordinating Center will prepare a computer-generated randomization schedule for treatment allocation. Patients will be randomized by a pre-validated and configurable system that is accessed via the internet or telephone. Patient stratification will occur according to clinical site.

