We also hypothesize that placebo has superior bleeding rates compared to LMWH based on the following assumptions: i) incidence of major bleeding in bridging group is 3.0%; and ii) incidence of major bleeding in no bridging group is less than the bridging group. If we assume that the incidence of major bleeding is ~3.0% for the LMWH group, as derived from our background work, 1.0% in the placebo group (as derived from trials where patients received warfarin alone after surgery [27]), and a 2-tailed alpha of 0.05, the proposed trial (with 1,641 patients per arm) has 98.8% power to detect superiority for the bleeding endpoint. The figures represent the required sample size per group, based on a power of 80%, and a 2-tailed alpha of 0.05, to detect differences in various incidences of major bleeding between the bridging group and "no bridging" group.

Bleedin	ng in Pla	cebo (No E	Bridging) Arm
0.5%	1.0%	1.5%	2.0%
769	2237	11194	
486	1138	3028	14209
344	772	1488	3788
262	508	914	1828
209	384	640	1113
	0.5% 769 486 344 262	0.5%1.0%76922374861138344772262508	769223711194486113830283447721488262508914

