7.0 Potential Co-Interventions

7.1 Concomitant Antiplatelet Therapy

A considerable proportion of patients who are screened for this trial use concomitant antiplatelet therapy with warfarin. For example, low-dose aspirin (\leq 100 mg per day) is used by approximately 25% of patients with chronic atrial fibrillation who, typically, have concomitant coronary artery disease or other arterial vascular disease [38]. Antiplatelet drugs are also standard of care for some procedures, such as percutaneous coronary interventions, and mandating interruption of antiplatelet therapy in these settings would make the Trial results less applicable to "real world" clinical practice. Specifying separate protocols for periprocedural interruption of aspirin, clopidogrel and/or other antiplatelet drugs would also add complexity, impair study feasibility, and increase the potential for protocol violations.

Power calculations usually assume that events occur homogeneously across an entire group (either treated or placebo). However, it is possible that patients on aspirin or other antiplatelet drugs could have higher expected bleeding rates than the rest of the study population. Although these patients will be randomized to bridging anticoagulation or placebo, the potential exists for the antiplatelet subjects to be assigned unequally between the two arms by play of chance. To address this concern, we have conducted statistical simulations of the effect of antiplatelet therapy on the proposed trial design, demonstrating that concomitant antiplatelet therapy will not significantly alter the statistical power of the trial or its alpha level Consequently, for this trial, *the management of perioperative antiplatelet drug therapy will be left to the discretion of the treating clinician*.

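### Randomization is stratified by clinical site, but major bleeding and the secondary endpoints are tested on pooled tables that ignore site; the test is valid but slightly conservative if sites differ

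*Combined protocol and SAP*

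**What the plan says.** Section 5.5.2 names one stratification factor: "Patient stratification will occur according to clinical site". It gives no block size or number of sites.

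For major bleeding, section 5.12.2 says "we will use the simpler Fisher's mid-p test [40] to test significance". Its reason is that confidence limits are not needed for this endpoint. Sections 5.12.3 and 5.12.4 use the same test for myocardial infarction, deep vein thrombosis, pulmonary embolism, death and minor bleeding. No stratum or covariate is named for any of them. The sensitivity analyses in 5.12.6 are time-to-event analyses and mention neither site nor covariates.

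The design assumptions for bleeding are in 5.11.2: "incidence of major bleeding is ~3.0% for the LMWH group" and "1.0% in the placebo group (as derived from trials where patients received warfarin alone after surgery [27]), and a 2-tailed alpha of 0.05". The result given there is that "the proposed trial (with 1,641 patients per arm) has 98.8% power to detect superiority for the bleeding endpoint".

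Two other baseline items bear on bleeding. Section 5.3 says "Patients who satisfy the trial eligibility criteria will be classified according to the planned surgery/procedure", and that class sets when study drug restarts (5.7.3.2). Section 7.1 says of antiplatelet users that "the potential exists for the antiplatelet subjects to be assigned unequally between the two arms by play of chance". It then reports simulations that found no significant effect of antiplatelet therapy on power or alpha.

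**The concern.** The usual principle is to analyse as randomized. Where allocation is balanced within sites, differences between sites cannot contribute to the difference between arms. A single pooled 2x2 table still counts those differences as noise. Its reference distribution is then too wide, so the test rejects less often than its nominal 5% and gives up some power. The error goes one way only, towards missing a difference in bleeding. A site-stratified test avoids this with data the trial already holds.

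The point concerns 5.12.2 to 5.12.4. It does not extend to the non-inferiority analysis of arterial thromboembolism in 5.12.1.

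**Working it through.** **Inputs from the documents.** Major bleeding 3.0% v 1.0%, 1,641 per arm, two-sided alpha 0.05, stated power 98.8% (5.11.2). Mid-p size about 0.0481 at an event rate near 1% (5.12.6). Antiplatelet use about 25%, given for low-dose aspirin (7.1).

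**Inputs assumed.** Number and size of sites, spread of bleeding risk between sites, and balance of arms within sites.

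**1. The plan's own figure.** Power is the sum over all (x, y) of Bin(x; 1641, 0.03) × Bin(y; 1641, 0.01), counting tables whose two-sided mid-p is at most 0.05. Here mid-p = 2 × (smaller tail − ½ × probability of the observed table). The result is 98.83%, which matches 98.8%. At the planned enrolment of 1,813 per arm it is 99.3%. With no site differences, exact size at 1,641 per arm is 0.0477, 0.0489 and 0.0493 at event rates of 1%, 2% and 3%.

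**2. Why pooling is conservative.** Per patient, the pooled variance is p(1 − p). The variance relevant under within-site balance is p(1 − p) − Var(p_site). With log-normal site risks of log-scale SD s, Var(p_site) = p²(exp(s²) − 1). The share of variance overstated is therefore r = p(exp(s²) − 1)/(1 − p), and the size becomes 2 × [1 − Φ(1.96/√(1 − r))].

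| p | s | r | size |
|---|---|---|---|
| 2% | 0.5 | 0.02 × 0.284/0.98 = 0.6% | 0.0493 |
| 2% | 1.0 | 0.02 × 1.718/0.98 = 3.5% | 0.0460 |
| 3% | 0.5 | 0.03 × 0.284/0.97 = 0.9% | 0.0490 |
| 3% | 1.0 | 0.03 × 1.718/0.97 = 5.3% | 0.0440 |

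The loss grows with the event rate. At p = 0.5% and s = 1.0, r is only 0.9%.

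**3. Simulation for major bleeding.** Arms were equal within each site: 60 sites of 27 per arm (1,620) or 100 sites of 16 per arm (1,600). There were 40,000 trials per null case and 20,000 per power case. Each cell gives pooled mid-p / site-stratified Mantel-Haenszel without continuity correction.

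| Sites | s | Size at 2% | Size at 3% | Power 3% v 1% | Power 3% v 1.75% |
|---|---|---|---|---|---|
| 60 | 0 | 0.048 / 0.049 | 0.050 / 0.050 | 98.7 / 98.7 | 65.3 / 65.6 |
| 60 | 0.5 | 0.047 / 0.049 | 0.048 / 0.050 | 98.6 / 98.7 | 64.4 / 65.1 |
| 60 | 1.0 | 0.044 / 0.049 | 0.043 / 0.049 | 98.4 / 98.5 | 64.8 / 66.3 |
| 100 | 0 | 0.048 / 0.049 | 0.050 / 0.050 | 98.6 / 98.7 | 64.2 / 64.6 |
| 100 | 0.5 | 0.049 / 0.051 | 0.048 / 0.049 | 98.7 / 98.7 | 63.6 / 64.3 |
| 100 | 1.0 | 0.044 / 0.049 | 0.044 / 0.051 | 98.4 / 98.6 | 64.5 / 66.2 |

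At 3% v 1.75% the gain is 0.4 to 0.7 point for s up to 0.5, and 1.5 to 1.7 points at s = 1.0. About 0.4 point of this appears even at s = 0. That part comes from replacing mid-p by Mantel-Haenszel, not from stratifying.

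**4. Looser within-site balance.** With 91 assumed sites, blocks of 4, equal or skewed site sizes and a site SD of 1.0, pooled size is about 0.045 to 0.047 against 0.048 to 0.051 stratified. The power gain is 0.1 to 0.2 point at 3% v 1% and 0.7 to 0.9 point at 2% v 1%. With no site differences, stratifying lost nothing detectable.

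**5. Minor bleeding, illustration only.** The documents give no rate, so 10% to 20% is assumed, with 91 sites of 18 per arm and a normal score test standing in for pooled mid-p. Pooled size is 0.045 to 0.048 at a log-odds SD of 0.5 and 0.035 to 0.039 at 1.0; stratified it is 0.049 to 0.051 in both cases. At 15% with an odds ratio of 1.3, power is 77.6% pooled v 78.5% stratified (SD 0.5) and 69.8% v 74.1% (SD 1.0).

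**6. Covariate imbalance.** With a factor of 25% prevalence and an assumed relative bleeding risk of 1.5 to 5, pooled mid-p keeps a size of 0.048 to 0.050. Its power at 3% v 1% is 98.8% to 98.9%, against 98.8% to 99.0% when stratified on the factor. For procedure class, assume 30% major and an odds ratio of 4. A 2-SD imbalance is 2 × √(2 × 0.3 × 0.7/1641) = 3.2 points. Multiplied by a 3.1-point difference in risk between classes, it moves the bleeding difference by 0.10 percentage point. The standard error is √(2 × 0.02 × 0.98/1641) = 0.49 point, so the shift is 0.2 SE.

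**The case against.** The strongest reply is that a valid, simple test was chosen and nothing at the design effect depends on the choice. That stands: size never exceeds its nominal level materially, and power for 3% v 1% is 98% to 99% either way. The larger gains need a weaker effect and wide site differences. They also rest on inputs the documents do not give, including how tightly arms are balanced within sites. With looser balance the conservatism shrinks.

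A reader might infer that the plan concedes uneven bleeding-risk groups and then ignores them. The documents do not support this. Section 7.1 speaks only of antiplatelet users, and it reports simulations with a reassuring conclusion, which step 6 agrees with. Their inputs and results are not shown, but that is a lesser matter. Nor does chance imbalance bias an unadjusted randomized comparison: over repeated randomization its 5% level already allows for it.

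A reader might also expect one stratified test to cure low size, lost power and covariate imbalance together. It would not. Stratifying by site does nothing about procedure class or antiplatelet use, and adjusting for those two does nothing about site.

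What remains is that the plan gives no reason for leaving out its only randomization stratum, and that including it costs almost nothing.

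**Conclusion.** The mismatch between site-stratified randomization and pooled testing is real and its consequence is small. The pooled Fisher's mid-p is valid and the 98.8% power claim holds. If bleeding differs between sites, the size for major bleeding falls to about 0.043 to 0.049, depending on the assumed spread. The power lost is at most about 0.2 point at 3% v 1% and up to roughly 1 to 1.7 points at weaker effects. The loss could be larger for a commoner endpoint such as minor bleeding, but that rests on an assumed event rate. For rare secondary endpoints it is negligible. All sizes depend on assumed site numbers, site spread and within-site balance. This is an improvement worth making, not an error that threatens the trial's conclusions.

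**What to change.** In 5.12.2, and likewise in 5.12.3 and 5.12.4, pre-specify one test stratified by clinical site as randomized. Either a Mantel-Haenszel test or a stratified exact conditional mid-p test would serve. Fix the choice in advance for all these endpoints, so that the test does not depend on how many events occur. State a rule for very small sites, for example that sites below a set size are pooled. Note also that a site with no events, or with patients in one arm only, contributes nothing. Keep the pooled Fisher's mid-p as a supporting result.

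Optionally, add one pre-specified supportive analysis of major bleeding adjusted for planned minor/major class and baseline antiplatelet use, described as a small precision gain. Showing the inputs and results of the simulations in 7.1 would help the reader.

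The cost is a few sentences in the analysis plan and a few lines of code, settled before unblinding. No new data, patients or visits are needed.

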5.12.4 Secondary bleeding endpoint analyses

Minor bleeding event rates will be analyzed using Fisher's mid-p test.

5.12.5 Interim analyses

Three interim analyses for safety and two interim analyses for efficacy will be performed. The first safety analysis will be performed when safety endpoint information is available for 20 percent of the patients. A second and third safety analysis will be performed when 50 percent and 75 percent of the patients respectively have endpoint information. The first efficacy analysis will be performed when primary endpoint information is available for 50 percent of the patients. A second efficacy analysis will be performed when 75 percent of the patients. A second efficacy analysis will be performed when 75 percent of the patients.

The trial will be stopped for efficacy only for overwhelming evidence in favor of placebo or in favor of bridging anticoagulation. Specifically, the trial will be stopped in favor of placebo if:

- the primary efficacy endpoint significantly favors placebo at the 0.01 level, and
- the primary safety endpoint significantly favors placebo at the 0.01 level.

The trial will be stopped in favor of bridging anticoagulation if:

- the primary efficacy endpoint significantly favors bridging anticoagulation at the 0.01 level, and
- the primary safety endpoint significantly favors bridging anticoagulation at the 0.01 level.

Because these stopping rules are symmetric, the interim analysis results will be provided to the DSMB in a blinded fashion. The DSMB will take the above rules and guidelines into account when formulating its charter, and has the authority to recommend termination of the trial even if the above guidelines are not met exactly.

The final analysis for efficacy will not require any adjustment for the interim looks, assuming that the trial was not stopped early. Note that the interim analyses are for superiority, but the final analysis is for non-inferiority. The two interim analyses (taking each endpoint separately) spend a total alpha of 0.017. The final analysis spends a total alpha of 0.05. Based on the theory of intersection-union tests, the overall study alpha is the maximum of 0.017 and 0.05. [41,42] Thus the nominal study-wide alpha level for efficacy is 0.05.

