9.7 Data and Safety Monitoring Board (DSMB)

The National Heart, Lung and Blood Institute DSMB adheres to all National Institutes of Health (NIH) regulations and policies including the Data and Safety Monitoring Policy found on the website at http://www.nhlbi.nih.gov/funding/policies/dsmpolicy.htm.

The objectives of the Board are to periodically review the trial data to assess the safety of bridging using delteparin in this patient population and to assure the integrity and proper conduct of the trial. The DSMB may recommend discontinuation of the trial, or modifications of the study protocol for safety reasons.

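### Section 5.12.5 has no working pre-specified boundary for excess ATE on placebo, because a stop in favor of bridging also requires bleeding to favor bridging

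*Combined protocol and SAP*

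**What the plan says.** Section 5.12.5 plans safety looks at 20%, 50% and 75% of patients and efficacy looks at 50% and 75%. It frames the rule as follows: "The trial will be stopped for efficacy only for overwhelming evidence in favor of placebo or in favor of bridging anticoagulation". A stop in favor of bridging has two joint conditions: "the primary efficacy endpoint significantly favors bridging anticoagulation at the 0.01 level, and" "the primary safety endpoint significantly favors bridging anticoagulation at the 0.01 level". The stop in favor of placebo is the mirror image. No numerical criterion is attached to the safety looks, and no boundary on ATE alone appears.

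The section then sets out how results are shown: "Because these stopping rules are symmetric, the interim analysis results will be provided to the DSMB in a blinded fashion". The DSMB is to take the rules into account in its charter, and it "has the authority to recommend termination of the trial even if the above guidelines are not met exactly".

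Section 9.7 gives the DSMB the task "to periodically review the trial data to assess the safety of bridging using delteparin in this patient population" and adds: "The DSMB may recommend discontinuation of the trial, or modifications of the study protocol for safety reasons".

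Section 5.11.2 states the bleeding hypothesis: "incidence of major bleeding in no bridging group is less than the bridging group", with working rates of 3.0% on LMWH and 1.0% on placebo. Section 2.0 makes excess ATE without bridging the risk that the trial has to exclude.

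**The concern.** The two foreseeable harms lie in opposite arms: ATE where bridging is withheld, bleeding where dalteparin is given. A rule that needs both endpoints to favor the same arm covers neither the pattern the protocol expects for bleeding nor the pattern that would matter most for placebo patients, namely more ATE on placebo together with more bleeding on bridging. If the bleeding hypothesis is right, the bleeding condition blocks the stop in favor of bridging however large the ATE excess becomes. Patients could then go on being randomized to placebo after a clear ATE excess, with no written criterion telling the DSMB when to act.

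**Working it through.** **Inputs.** From 5.11.1: ATE 1.0% on bridging and a margin of 1.0 point, so placebo ATE of 2.0% sits at the margin. From 5.11.2: bleeding 3.0% on bridging and 1.0% on placebo, 1,641 per arm. From the synopsis: 1,813 per arm planned. From 5.12.2: Fisher's mid-p test for bleeding. From 5.12.5: level 0.01, efficacy looks at 50% and 75%.

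**Assumptions.** Section 5.12.5 names no interim test and no sidedness, so I used mid-p, two-sided, for both endpoints. ATE and bleeding are simulated as independent. Placebo ATE of 3% and 4% is assumed.

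**The plan's own figure.** Exact enumeration of two binomials (1,641 per arm, 3.0% vs 1.0%, mid-p, two-sided 0.05) gives bleeding power of 98.83%. The stated 98.8% reproduces.

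**The bleeding condition alone.** At the 50% look (820 per arm) the expected bleeds are 0.03 × 820 = 24.6 on bridging and 0.01 × 820 = 8.2 on placebo. The rule needs the reverse, at 0.01. The exact probability is about 1.5 × 10⁻⁸ at the 50% look and below 10⁻⁹ at the 75% look (1,231 per arm). The joint rule cannot be met more often than its bleeding condition. These figures therefore cap it whatever the ATE rates, and whatever the dependence between endpoints.

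**The rule in simulation** (400,000 trials per scenario, 1,641 per arm, bridging ATE 1%):

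| Placebo ATE | Written rule, bleeding 1% placebo / 3% bridging | Written rule, bleeding 3% / 3% | ATE alone at 0.01 |
|---|---|---|---|
| 2% | 0 | 0.2% | 31–32% |
| 3% | 0 | 0.6% | 86% |
| 4% | 0 | 0.7–0.8% | 99% |

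At 1,813 per arm the written rule again never fires at 1% / 3% bleeding, and ATE alone crosses in 35–36%, 90% and more than 99%.

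**One concrete look.** Take 23 ATEs on placebo and 8 on bridging among 820 per arm, that is 2.80% vs 0.98%. The pooled rate is 31/1,640 = 0.0189. Then z = 0.01829 / √(0.0189 × 0.9811 × 2/820) = 0.01829 / 0.00673 = 2.72, and the mid-p value is 0.0065. The rule would still not be met unless bleeding also favored bridging at 0.01.

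**Cost of an ATE-only guideline.** At ATE 1% / 1% it crosses in about 0.7% of trials. About 5 to 6% of those would have met non-inferiority at the end (Wald 95% limit, as an approximation to the exact limit of 5.12.1). The loss is 0.007 × 0.055 ≈ 0.0004, or 0.04 points of power. At 2% vs 1%, fewer than 0.01% of crossing trials would have met non-inferiority; at 3% or 4% vs 1%, none did.

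**Where the cost is larger.** At low rates a difference can be significant and still lie inside an absolute margin of 1 point. Seven ATEs against none among 820 per arm gives a two-sided mid-p of 2 × ½ × C(820,7)/C(1640,7) ≈ 0.008, yet the observed excess is 7/820 = 0.85 points. In simulation at 0.5% / 0.5%, about 42% of crossing trials would still have met the margin. At an assumed 0.5% placebo vs 0.1% bridging, 17% of trials cross and 45% of those would have met it, a loss of about 7.8 points of power.

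**The case against.** The strongest reply is that the joint rule is a guideline for efficacy stopping, not the only route to a stop. Section 5.12.5 lets the DSMB act outside the guideline, and 9.7 lets it recommend discontinuation for safety. The charter is not among the documents. A reader might infer that the trial has no working stop for excess ATE; the documents do not support that. What they lack is a pre-specified boundary. The gap still matters, because the charter is to be written with these rules in view. Acting on ATE alone would also mean setting aside a whole required condition, not allowing for a near miss.

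Oversight between looks also exists. Under 5.8 a suspected ATE is documented within 24 hours, and under 11.1.8 each SAE report goes to the DSMB chair within 1–2 business days. These are single reports, not comparisons between arms.

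A reader might infer that blinded results would hide an imbalance. Rules that can favor either arm need data split by arm, so coded arms are the natural reading, and coded arms would show a difference. The weakness is narrower: blinding is justified by a symmetry of the rules that the expected harms do not share, and neither rule covers one arm having more ATE while the other has more bleeding.

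A reader might also infer that non-inferiority is always lost once ATE crosses 0.01. That is nearly exact at 1% on bridging but fails at low rates, as shown above, and 3.4 and 4.3 cite rates of 0.7% and 0.8%. Placebo ATE of 3% or 4% appears nowhere in the protocol. At the margin itself the ATE-only guideline would fire in only about a third of trials.

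Finally, the endpoint is ATE (ischemic stroke, TIA, systemic embolism), not stroke alone. Section 3.4 argues that ATE risk is similar with and without bridging, so the excess is a risk to be guarded against and not one the protocol predicts.

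**Conclusion.** The point holds in this form: 5.12.5 contains no working pre-specified boundary for excess ATE on placebo. Under the protocol's own bleeding rates the stop in favor of bridging has a probability of about 1.5 × 10⁻⁸ or less at each look, and even with equal bleeding of 3% it fires in under 1% of trials at the placebo ATE rates examined. This is a stated rule that cannot do its job, not an omitted detail. Protection rests on DSMB discretion, exercised under a guideline that speaks only to both endpoints favoring one arm, with a remit in 9.7 that names the safety of bridging but not of withholding it. The cap on the rule depends only on the 3% / 1% bleeding rates and the test at 0.01. The ATE-alone percentages depend on the assumed placebo rates. An unseen charter could already close the gap.

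**What to change.** In 5.12.5, remove the bleeding condition from the stop in favor of bridging. State instead a non-binding harm guideline for the 50% and 75% looks: ATE favors bridging at two-sided p<0.01, whatever the bleeding result. Have it read with the 1% margin, for example by also requiring that the observed excess or the conditional power makes final non-inferiority unlikely. Tabulate ATE by arm at the 20% look. As a secondary change, let the DSMB see identified arms, since the guideline is then asymmetric. Carry the same text into the charter, or cite the charter if it already has such a boundary.

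The cost is protocol and charter wording and no extra patients. Power falls by about 0.04 points at ATE 1% / 1%. It falls by more if ATE rates are well below 1% and the margin check is left out (about 7.8 points at an assumed 0.5% vs 0.1%). Stopping for ATE harm can only remove non-inferiority claims, so it cannot inflate the type I error of the final analysis, which stays as planned.
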